8.1 Subject Accrual

The maximum sample size for the study is 2,320 subjects. We estimate that sample size is achievable in a timely fashion if we enroll an average of 1 patient/site/month, distributed across 50 enrolling sites. For the feasibility assessment phase, if the enrolling sites achieve >70% of this rate (> 0.7 patients/site/month), then the feasibility guideline for patient accrual will have been met. A site will be defined as “started” when the site indicates that they have begun

screening, and the #patients/month/sites will be calculated as the number of patients enrolled across all sites, divided by sum of the screening months among the site, and number of sites. A calendar month is defined by the number of days passed since the initiation of screening, divided by 30. If a site withdraws from the study, then they will stop contributing patients and calendar months.

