Optimal resuscitation strategies for patients with sepsis-induced hypotension have been debated for decades. Critical questions are (a) whether to rely primarily on intravenous fluids (versus vasopressors), (b) how to optimally titrate the volume of fluid administered, and (c) whether vasopressors should be started earlier to spare the patient from large volumes of fluid. These key questions are relevant to hundreds of thousands of critically ill patients every year. Cross-national practices vary widely. Because individual clinicians hold strong opinions on the matter, observational studies remain hopelessly confounded by indication. Only randomization can persuasively disentangle the effects of strategies favoring fluids versus vasopressors.

The Crystalloids Liberal Or Vasopressors Early Resuscitation in Sepsis (CLOVERS) trial is a large (n=2,320) nationwide multi-center randomized clinical trial by the NHLBI-sponsored PETAL network to test whether an early “wet” fluid-intensive/pressor-restrictive strategy improves 90-day in-hospital mortality in patients with sepsis-induced hypotension, compared to an early “dry” fluid-restrictive/pressor-intensive strategy. CLOVERS presents a unique and fleeting opportunity to definitively measure patient-centered outcomes caused by markedly different initial resuscitation strategies. CLOVERS will enroll over 3 years, starting March 2018.

The pragmatic CLOVERS design focuses on hospital outcomes. Thus, CLOVERS will not address key patient-centered controversies that are prominent in the literature:

Cognitive Impairment: An ancillary study of the NHLBI-funded Fluid and Catheter Treatment Trial (FACTT) showed that randomization to a dry strategy in patients with ARDS was associated with impaired memory, verbal fluency, and executive functioning—with a quadrupling of the odds of cognitive impairment (71% cognitively impaired vs 38%, OR: 4.0 (95% CI: 1.5–10.6)) despite identical in-hospital mortality—but, in a sample of just 75 survivors of ARDS, not all with sepsis.

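### The accrual rate in Protocol Section 8.1 counts sites twice, so an on-target network scores 1/(number of sites); separately, the planned rate does not match the 3-year enrolment in Appendix J

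*Protocol*

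**What the plan says.** Protocol Section 8.1 gives the size of the trial ("The maximum sample size for the study is 2,320 subjects") and calls it achievable in good time "if we enroll an average of 1 patient/site/month, distributed across 50 enrolling sites". It names no enrolment period. The accrual guideline counts as met "if the enrolling sites achieve >70% of this rate (> 0.7 patients/site/month").

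The metric is then defined. Its numerator is the enrolment total of the whole network. The rest of the sentence gives the denominator: "divided by sum of the screening months among the site, and number of sites". Two further sentences say how months are counted: "A calendar month is defined by the number of days passed since the initiation of screening, divided by 30", and "If a site withdraws from the study, then they will stop contributing patients and calendar months".

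Section 8 lists accrual as one of three feasibility parameters, beside compliance and separation. The protocol committee recommends continuing, modifying or halting; the steering committee decides and the DSMB reviews. Section 8.3 allows the trial to be stopped at 100, 200 or 300 patients for lack of feasibility, and enrolment rates are among the grounds.

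The only enrolment duration is in Appendix J, the SHAMROC ancillary study: "CLOVERS will enroll over 3 years, starting March 2018".

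**The concern.** A rate per site per month needs one denominator: the months of screening summed over sites. Section 8.1 forms that sum and then divides by the number of sites as well. The result is no longer in the units of the 0.7 mark, and at a constant true rate it falls as sites open. At stake is a pre-specified feasibility criterion that, followed to the letter, would report a healthy network as far below target at a look where stopping is an option.

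The second issue is the timetable. Section 8.1 and Appendix J describe the same trial at the same maximum size, but the rate in one does not produce the duration in the other. Anyone planning staffing, funding or ancillary follow-up from 3 years would be working with a period that the planned rate cannot deliver at full enrolment.

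**Working it through.** **Inputs.** From Section 8.1: maximum sample size 2,320; planned rate 1 patient/site/month; 50 sites; guideline above 70% of plan; month = 30 days. From Appendix J: 3 years, taken as 36 months. From Section 9.1, Table 3: cumulative stopping probabilities at 773, 1,547 and 2,320 patients.

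**The plan's own threshold.** 0.70 × 1 = 0.7 patients/site/month. This reproduces.

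**The metric.** Let P be patients enrolled, M the sum of screening months over sites and S the number of sites.
- Rate in the stated units: P / M.
- Rate as written: P / M / S.

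Exactly on target, P = M, so the written metric equals 1/S. Elapsed time and staggered opening of sites cancel out.

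| Sites started | P / M on target | As written (1/S) | True rate needed for the written metric to exceed 0.7 (0.7 × S) |
|---|---|---|---|
| 1 | 1.00 | 1.00 | 0.7 |
| 2 | 1.00 | 0.50 | 1.4 |
| 10 | 1.00 | 0.10 | 7 |
| 50 | 1.00 | 0.02 | 35 |

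An example inside the feasibility phase: 50 sites screening for 6 months at target give 300 patients and 300 site-months. The intended rate is 300/300 = 1.00, which passes. The written metric is 300/300/50 = 0.02, which does not.

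**The timetable at full enrolment.**
- Months to 2,320 at plan: 2,320 / (50 × 1) = 46.4, or 46.4/12 = 3.9 years. With 30-day months: 46.4 × 30/365.25 = 3.8 years.
- Enrolled by month 36 at plan: 50 × 36 = 1,800.
- Rate needed for 2,320 in 36 months at 50 sites: 2,320 / (50 × 36) = 1.29 patients/site/month.

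**The timetable allowing for early stopping.** 2,320 is a group-sequential maximum.
- Under the alternative, Table 3 gives stopping probabilities of 0.06136 at stage 1 and (0.52878 + 0.01919) − 0.06136 = 0.48661 at stage 2, leaving 0.45203 for stage 3. Expected size: 773 × 0.06136 + 1,547 × 0.48661 + 2,320 × 0.45203 ≈ 1,849. At 50 a month that is about 37 months.
- Under the null, the probabilities are 0.00062, (0.00988 + 0.45174) − 0.00062 = 0.46100, and 0.53838. Expected size: 773 × 0.00062 + 1,547 × 0.46100 + 2,320 × 0.53838 ≈ 1,963. At 50 a month that is about 39 months.

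These expected sizes ignore patients enrolled while outcomes mature, and they assume that the non-binding futility boundary is followed.

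**The case against.** The strongest reply is that the double division is a slip which the same section resolves. Section 8.1 gives both the plan and the guideline in patients/site/month, and a twice-divided number cannot be compared with either. That stands as evidence of intent. It does not repair the formula: the month total is described as a sum, and a withdrawn site stops adding to it, so the months cannot be read as mean or elapsed months.

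A reader might infer that the criterion can never be met. That is too strong. With one site the formula is right, and two sites pass if the true rate exceeds 1.4. The failure belongs to realistic multi-site scale.

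A reader might also infer that a low score halts the trial. The documents do not say so. Section 8.1 states only what meets the guideline, Section 8 has three bodies review the data, and Section 8.3 makes stopping possible, not mandatory. Those bodies would probably question a score of 0.02 from a network enrolling 50 patients a month.

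On the timetable, it is tempting to say that the 0.7 floor is inconsistent with 3 years, because 2,320 / (50 × 0.7) = 66.3 months. The protocol never ties the floor to 3 years, and a floor set at 70% of plan must take longer than plan. The mismatch lies with the planned rate of 1.0. It is also fair that the 3 years is a single sentence in an ancillary-study appendix, and that expected enrolment under early stopping (about 37 to 39 months at plan) comes close to it. Neither point brings full enrolment below 46.4 months.

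**Conclusion.** The accrual metric is wrong as written. On target it returns 1/(number of sites) where it should return 1, which is 0.02 with 50 sites against a mark of 0.7. The result needs no assumption beyond reading the sentence literally. It is most likely a drafting error, and its reach is the feasibility assessment and its record. Section 8 keeps the feasibility looks separate from the interim and final efficacy analyses, so the primary analysis and type I error are untouched.

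The timetable mismatch is real but narrower: 46.4 months at plan against 36 stated, a gap of 10.4 months, with 2,320 − 1,800 = 520 patients still to enrol at month 36. It assumes 50 sites active throughout at 1 patient/site/month and enrolment to the maximum. Slower site opening would lengthen the period and an early stop would shorten it.

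Section 9.3 describes a change to the liberal arm as already made, so the feasibility looks may be over. The documents do not settle this. If they are over, the correction still matters as a record of how accrual was calculated.

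**What to change.** In Section 8.1, define the rate as total patients enrolled at all started sites divided by total site-months of screening, where a site's months are its days since screening began divided by 30, and delete the further division by number of sites. If feasibility looks have already taken place, add a line saying which calculation was used.

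In Appendix J, replace the 3-year period with about 46 months at the maximum sample size for 50 sites at 1 patient/site/month, and note that stopping at an interim analysis would shorten it. State the same period in Section 8.1 so that the two places agree.

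Leave the 0.7 floor as it is; re-basing it on a 3-year pace would be a preference, not a correction.

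The cost is one corrected sentence, one restated period and the acknowledgement of a longer timeline. Sample size, stopping boundaries and the analysis do not change.

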8.2 Compliance with Fluid Management Protocols

Compliance with the hemodynamic protocol instructions and the safety of the protocol will be monitored by the protocol oversight committee and DSMB. Detailed treatment data in regards to intravenous fluid administration, vasopressor use, vital signs, and the presence of protocol defined criteria for fluid and vasopressor administration will be collected hourly for the first 24 hours by the sites on a detailed flow sheet. We will assess protocol compliance (defined as following the protocol rules based on vital signs and actions) for the first 6 hours, and then randomly sample 4 other 1-hour time-points during the 24-hour treatment period. The compliance rate will be defined as the proportion of correct actions among the total actions performed; or $(\text{correct actions})/(\text{correct} + \text{incorrect actions}) \times 100$.

A “correct action” in the liberal group is defined as:

- a. Administration of the initial 2-liter fluid infusion within the first 180 minutes (if documented clinical assessment leads to a decision to administer less than two liters during the initial infusion or if the infusion time is deliberately lengthened, this is considered a correct action)
- b. Administration of a minimum 500cc fluid bolus when a “meets intervention criterion” is present
- c. Vasopressor use in the presence of a “rescue criterion”
- d. No fluid or vasopressor administration in the absence of a meets intervention criterion

An “incorrect action” in the liberal group is defined as:

- a. Failure to administer the initial 2-liter fluid infusion within the first 180 minutes (if clinical evaluation is that patient has normalized - fluids may stop and be considered a correct action).
- b. Failure to administer a 500cc fluid bolus when a “meets intervention criterion” is present and there is no contraindication (e.g. fluid overload or > 5 liters criteria already administered)
- c. Use of a vasopressor in the absence of a “rescue vasopressors recommended” criterion
NOTE: In both arms, fluids or vasopressors can be used at any time if the clinical team feels they are in the best interest of the patient. An incorrect action as defined in the protocol is not a protocol deviation but would be considered non-compliant for the purposes of compliance monitoring.

A “correct action” in the restrictive group is defined as:

- a. Initiation of vasopressors for SBP < 90mmHg and/or MAP <65mmHg within 60 minutes
- b. Titration of vasopressors to maintain MAP \geq 65mmHg
- c. Administration of a 500cc fluid bolus in the presence of a “rescue fluid” criterion
- d. Administration of fluid boluses to up to 2 liters of total fluid, including pre-randomization fluid,

at the discretion of the clinical team even where “rescue fluid” criteria are not met.

- e. No fluid or vasopressor administration/titration in the absence of a meets intervention criterion

An “incorrect action” in the restrictive group is defined as:

- a. Failure to initiate vasopressors for SBP < 90mmHg and/or MAP <65mmHg within 60 minutes
- b. Failure to titrate vasopressors for sustained (greater than 30 minutes) MAP < 65 mmHg
- c. Administration of intravenous fluid in the absence a “rescue fluids recommended” criteria
- d. NOTE: In both arms, fluids or vasopressors can be used at any time if the clinical team feels they are in the best interest of the patient. An incorrect action is not a protocol deviation but would be considered non-compliant for the purposes of compliance monitoring.

The goal is to achieve > 70% compliance with instructions across enrolling sites. Summative data will be shared with the protocol committee, steering committee, and the DSMB. During this period, the protocol rules may be refined through iterative application and evaluation in the enrolling sites. If compliance is lower than 70%, but the separation of intravenous fluid volumes and/or vasopressor use between groups is met, amendments may be considered to try to improve compliance, but the trial will be considered feasible and will continue.

To maintain blinding to outcomes, the reports will be aggregated without reference to patient number. They will not include any information beyond the 24-hour treatment protocol period. The protocol oversight committee, PETAL steering committee and/or the DSMB may ask that detailed iterative refinement continue at each 100 patient data completion marks during this phase. The protocol oversight committee and PETAL steering committee may also recommend based on the data from the 100 or 200 patient data completion marks that no further protocol modifications are indicated.

8.3 Separation of Groups Based on Fluid and Vasopressor Administration Data

Experimental separation of patients in the restrictive versus liberal arms will be closely monitored over the course of the first 300 enrolled patients, with staged evaluations at 100, 200, and 300 patients to allow modification of experimental protocols to improve compliance and/or experimental separation. The trial can be stopped at 100, 200, or 300 patients based on the below criteria if there is evidence of lack of feasibility by enrollment rates, protocol compliance, and/or anticipated separation.

A decision to move to the next phase of the trial will be based on the likelihood of meeting 2 of the following 3 separation guidelines at the end of the trial:

1. Difference of 1000cc (or greater) fluid administered over the first 6 hours of the treatment protocol
2. Difference of 1000cc (or greater) fluid administered over the first 24 hours of the treatment protocol

3. Difference of 3 hours (or greater) of mean time of vasopressor use over the first 24 hours of the treatment protocol

During each look at the 100, 200, and 300 patient data completion mark we will have the opportunity to modify the protocol to optimize recruitment, protocol compliance, and treatment group separation. Fluid separation at 6 and 24 hours will be analyzed as follows: we will regress the log of the fluids administered on the treatment group and report the difference in the exponentiated means between the treatment groups and the confidence interval of this difference. This estimate is equivalent to the difference in the medians under the log-normal distribution, but the confidence limits are narrower due to the use of a parametric model. If the fit to the log-normal distribution is poor, we will estimate the difference in medians using quantile regression. If changes to significantly improve separation are not likely, and the upper end of a 90% confidence interval on the difference in medians is less than 1 liter, we will consider recommending that the study be stopped. (Note: This is equivalent to a test of the hypothesis H_0 that the true difference is 1 liter, against the one-sided alternative that the true difference is less than one liter, with a one-sided p-value of 0.1).

During these looks, we will exclude data from patients managed by a no-longer-current protocol (i.e., in the event that a protocol change was implemented at the 100 or 200-patient marks). The goal is to preserve 90% power to detect a true separation between treatment arms in the overall trial of 1000ml at 6 and 24 hours. The stopping criteria will be based on the pooled mean and standard error of the log-transformed-fluid volumes.

Based on preliminary from a comparable study in Africa analyzed in this manner, and assuming no change in fluid strategy at earlier looks, at the 300-patient look, the stopping criteria would have a 90% probability of stopping the trial if the true separation was 0.6 Liters or less. We will deploy an analogous approach to assess a difference in vasopressor use of at least 3 hours within the 24-hour protocol period.

If at least 2 of 3 feasibility guideline parameters for separation are met, the separation parameter guideline is met. If none of the guideline parameters are met, the protocol oversight committee will recommend termination of the trial. If one of the parameters is met, then the protocol oversight committee will examine the data to determine whether there is adequate separation or if a protocol modification is likely to lead to increased separation. At each of the feasibility assessment evaluations, the protocol oversight committee will determine whether separation guidelines are adequately fulfilled and make a recommendation to the SC, and DSMB. The DSMB has final decision-making authority.

8.4 Assessment of Eligibility Criteria

We will assess the subset of patients enrolled with a qualifying blood pressure of $90 \leq \text{SBP} < 100$ mmHg, and the guideline feasibility parameters in this subset of patients. If during the feasibility assessment, data suggest that this group does not meet protocol compliance or separation guideline parameters, then this group may be excluded from the rest of the trial.

9. Statistical Considerations

9.1 Sample Size and Stopping Rules for Primary Outcome

The primary outcome is intention-to-treat 90-day all cause in-hospital mortality, where in-hospital includes both study and discharge hospitals (i.e. transfer hospitals or LTAC). Subjects who are discharged home (defined as residence prior to admission) prior to day 90 will be assumed to be alive at day 90.

Sample size is based on a comparison of binomial proportions with an overall two-sided alpha level of 0.05 and power of 0.90. With 15% mortality rate in liberal fluid group and 10.5% mortality rate in the restrictive group, maximum required total sample size is 2320 subjects.

The presumed 15% mortality rate in the liberal fluid group is based on several recently published clinical trials (Process [2], ARISE [3], Promise [4]).

This trial will stop for efficacy of either the restrictive or liberal fluid strategy arm, or futility. The study is designed with a symmetric group sequential t^4 alpha error spending function and a symmetric non-binding t^4 beta error spending function, where t is the information time, defined as the ratio of the effective sample size at the time of the look to the eventual sample size.

We plan to have two interim analyses and one final analysis that will be approximately evenly spaced. However, the scheduling of the DSMB meetings may alter this schedule.

Tables 1 and 2 present the stopping boundaries at each of the two interim analyses if they are equally spaced. The tables present stopping boundaries as either a one-sided p-value or an observed mortality difference. Table 3 presents the probability of stopping at each stage under the null (no effect of fluid) and alternative (restrictive fluid reduces mortality from 15% to 10.5%) hypotheses respectively.

Table 1. Stopping Boundaries: One Sided P Values

Stage	Sample Size	Lower Efficacy	Lower Futility	Upper Futility	Upper Efficacy
1	773	0.0003086	.	.	0.99969
2	1547	0.00479	0.27413	0.72587	0.99521
3	2320	0.02361	0.02361	0.97639	0.97639

Table 2. Stopping Boundaries: Mortality Differences

Stage	Sample Size	Lower Efficacy	Lower Futility	Upper Futility	Upper Efficacy
1	773	-0.08194	.	.	0.08194
2	1547	-0.04384	-0.01016	0.01016	0.04384
3	2320	-0.02742	-0.02742	0.02742	0.02742

Table 3. Cumulative Stopping Probabilities

Stage	Stop: Reject Null Given Null	Stop: Accept Null Given Null	Stop: Reject Null Given Alternative	Stop: Accept Null Given Alternative
1	0.00062	0.00000	0.06136	0.00000
2	0.00988	0.45174	0.52878	0.01919
3	0.04922	0.95078	0.89765	0.10235

For example, the second stage analyses will take place when approximately 1546 patients have been enrolled and the study would be stopped for efficacy if the 90-day absolute mortality difference is less than -0.044. This corresponds to a one-sided p-value of 0.00479. If the alternative hypothesis is true, then the probability of stopping for efficacy at this stage is 0.529.

On the other hand, if the absolute mortality difference at the second stage is less than 0.01, corresponding to a one-sided p-value between 0.274 and 0.726, then the study may be stopped for futility. If the null hypothesis is true, then the probability of stopping for futility at this stage is 0.452.

Table 4 below shows the effect of changes in the power of the study as a function of the mortality rate on the treatment with the higher mortality. We calculated the power under two assumptions. The first is that the absolute difference in mortality rates was 4.5% and the second was a 30% relative difference. The second row of the table shows the current assumptions. Whether the absolute or the relative difference is used, the power remains above 85%.

Table 4. Sensitivity to Assumed Null Mortality

Null Mortality	Power at 4.5% Absolute Decrease in Mortality	Power at 30% Relative Decrease in Mortality
17%	0.86	0.93
15% *	0.90	0.90
13%	0.94	0.85

*Assumption used in the CLOVERS Protocol

9.2 Power Calculation for 28-day Organ Support Free Days

We also note that CLOVERS is powered to detect meaningful differences in important secondary outcomes. For example, we believe that organ failure free days to day 28 (e.g. not intubated, nor receiving renal replacement therapy, and not on vasopressors after a 48-hour period of protocol washout) is a relevant and meaningful outcome. In fact, since this is a study where one must select an approach that will resemble one of the strategies (e.g. this is a test of existing therapies, not of a novel therapy that would require adoption) a meaningful difference in organ failure free days would be a meaningful study result that would alter treatment practices.

To demonstrate the power for organ failure free days – we use published data from the PROMISE trial (which reported organ failure free days). PROMISE reported organ failure free days to day 28 in usual care (mean +/- standard deviation) for cardiovascular (20.6 +/- 11.9), respiratory (19.8 +/- 12.0), and renal (20.6 +/- 11.9). We assume that organ failure free days (combining all three organ systems) would be largely determined by the worst of the three components. Since these components are all quite similar, we use a standard deviation of 12 organ failure free days for sample size calculations. Consistent with the FACTT trial, we identify 3 organ failure free days as clinically significant. Using a two-side alpha of 0.05 we obtain 90% power to detect a true mean difference as outlined in the table below:

Difference in Organ Failure Free Days	Total Patients
4	382
3	676
2	1516

